natural airway) was performed and demonstrated that 54.5% (24/44) experienced at least one desaturation value below 90%, and 29.5% (13/44) experienced at least one desaturation below 80%. Given the incidence of desaturation events of 54.5% and serious desaturation events of 29.5%, it is clear that the current methods utilized to oxygenate patients undergoing these procedures may have the potential for improvement.

8) Experimental design and data analysis, including inclusion and exclusion criteria, statistical basis for the number of subjects to be enrolled, the statistical plan for analyzing at least the primary hypothesis, matrix showing procedure plan for each study visit, data safety monitoring plan (4 pages maximum)

We aim to enroll approximately 40 pediatric patients scheduled to undergo otolaryngologic or endoscopic surgeries or procedures under general anesthesia. At the time of enrollment, patients will be randomized to control or intervention arms using a random number generator.

The incidence of desaturation events <90% during microdirect laryngoscopy procedures under general anesthesia at our institution over the previous 3 months has been reviewed and found to be 54.5% of cases. Given an estimated reduction in desaturation events by approximately 75%, we will plan to enroll a total of 40 patients (20 in each arm) for a power of 80%.

Inclusion criteria: Pediatric patients <18yo undergoing general anesthesia for procedures or surgeries at Lucile Packard Children's Hospital.

Exclusion criteria: Pregnancy, absence of parent or legal guardian able to provide written consent for study participation, anatomical or surgical contraindications (epistaxis, basilar skull fractures or abnormalities, nasal surgery or obstruction, nasal fractures, nasal vascular abnormalities), congenital heart disease with admixture physiology, baseline oxygen saturation < 94%, emergent surgery for which application of HFNC might delay surgery or might result in increased aspiration risk.

9) Significance (1 paragraph or less)

With this study we hope to determine whether THRIVE is superior to current oxygenation and ventilation techniques utilized during general anesthesia without an advanced airway device, and determine whether the use of THRIVE can prevent adverse events such as oxygen desaturation and its sequelae. We also hope to verify the safety of the use of HFNC during general anesthesia in pediatric patients.

10) Key references

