# **Transnasal Humidified Rapid-Insufflation Ventilatory Exchange (THRIVE) Use in Pediatric Populations**

## **Statistical Analysis Plan**

**NCT03430206**

**July 9, 2020**

After IRB approval, patients were randomized to control or THRIVE. Controls received 100% oxygen via the side port of a Parson's laryngoscope to insufflate the oropharynx at 6-10 L/min, titrated by the anesthesiologist. THRIVE received 100% oxygen via HFNC at 2L/kg/min using an Optiflow machine. Inclusion criteria were all patients from birth to 18 years old. Exclusion criteria included papillomatosis, tracheostomy, or unrepaired heart disease.

The primary aim was surgical interruptions. A priori power calculation based on 15 pilot surgeries demonstrated the frequency of interruptions in the control to be 0.93 and 0.33 in THRIVE. Assuming a Poisson regression, 80% power, and 95% confidence interval, 27 patients in each group (54 total) were needed to demonstrate a significant difference. To account for incomplete data and dropouts, an additional 20 patients (74 total) were targeted for consent. The secondary aims were to compare differences in oxygen desaturation index (ODI), desaturations below 90%, transcutaneous carbon dioxide (tCO2), and adverse events.

Demographics and postoperative diagnoses in control and THRIVE were collected. Interruptions were defined as the need to pause surgery to provide airway support, such as mask ventilation or intermittent intubation. Pulse oximetry was recorded by second in the electronic medical record. ODI was defined as a 4% decrease in saturation from a 120 second rolling mean for greater than 10 seconds. TCO2 was recorded at procedure start and end. Adverse events (nausea, vomiting, sinus pain, throat pain, epistaxis) were recorded prior to discharge.

Outcomes were calculated using negative binomial regression with case duration as an offset in the unadjusted and adjusted models, with the exception of tCO2. Models were adjusted for postoperative diagnoses. As a result of interim analysis, it was determined that analysis of the outcome measure Absolute Incidence of Oxygen Desaturation Less than 90% would not provide statistically meaningful results when comparing the two groups, and this outcome was removed from the analysis plan.

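### Does a pilot of 15 surgeries that cannot yield both 0.93 and 0.33 undermine the sample size of 27 per group?

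*SAP*

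**What the plan says.** The power paragraph of the SAP reads "A priori power calculation based on 15 pilot surgeries demonstrated the frequency of interruptions in the control to be 0.93 and 0.33 in THRIVE". It continues: "Assuming a Poisson regression, 80% power, and 95% confidence interval, 27 patients in each group (54 total) were needed to demonstrate a significant difference". Another 20 patients were added for incomplete data and dropout, giving 74 to be consented. An interruption is a pause in surgery for airway support, so the outcome is a count per case. The final paragraph of the SAP gives the analysis model: "Outcomes were calculated using negative binomial regression with case duration as an offset".

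The protocol mentions no pilot on interruptions. Its section 7 reports a retrospective series of 44 cases on desaturation, which "demonstrated that 54.5% (24/44) experienced at least one desaturation value below 90" percent. Its section 8 sizes the trial on that outcome: "Given an estimated reduction in desaturation events by approximately 75%, we will plan to enroll a total of 40 patients". The protocol is dated January 2018 and the SAP July 2020.

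Neither document says how the 15 surgeries were divided, whether 0.93 and 0.33 are per surgery or per unit of time, or whether pilot patients count towards the 54 or the 74.

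**The concern.** A mean number of interruptions per surgery is a whole number divided by the number of surgeries in that group. That makes the pilot figures checkable, and on the plain reading of 15 surgeries in all they fail the check. They are also the only stated basis for the primary sample size.

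A more serious worry follows. The pilot has the trial's two arms, and 15 per group would mean 30 surgeries. If those patients were also counted in the 54, then 30/54 = 56% of the primary data would be the data that set the assumed effect and the sample size. One could then doubt whether the 5% level of the primary test still holds.

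**Working it through.** **Inputs.** All are from the SAP's power paragraph: rates 0.93 (control) and 0.33 (THRIVE), Poisson counts, 80% power, 27 per group. A two-sided 5% level is inferred from the 95% confidence interval. Exposure is set to one unit per patient.

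**1. The plan's own figure.** The rate-difference formula is n = (z₀.₉₇₅ + z₀.₈₀)² (λ₁ + λ₂) / (λ₁ − λ₂)², with (1.960 + 0.842)² = 7.849.

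- 7.849 × (0.93 + 0.33) / (0.60)² = 27.47 per group.
- Log rate ratio with pooled null variance: 25.16. Square-root transform: 25.81. Conditional binomial: 25.52. Wald log rate ratio: 30.02.
- Simulated power at 27 per group (400,000 runs): Wald 80.4%, score 81.7%, likelihood ratio 82.1%.

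The stated 27 is reproduced within ordinary differences between methods.

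**2. Whole-count check on 15 surgeries in all.** With at most 14 surgeries in the control group, only 13/14 = 0.929 rounds to 0.93. That leaves one THRIVE surgery, whose mean must be a whole number. In the other direction, 0.33 needs a THRIVE group of 3, 6, 9 or 12, leaving 12, 9, 6 or 3 controls, and none of these gives 0.93. So 0 of the 14 splits fit; the result is the same if the figures were truncated rather than rounded.

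**3. What does fit.** Fifteen per group gives 14/15 = 0.933 and 5/15 = 0.333. Under rounding, unequal pairs such as 14 + 3 (total 17), 15 + 3 and 14 + 6 also fit. Rates per unit of time, model-based estimates, or 15 surgeries each observed under both techniques are not bound by the check.

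**4. Effect on the sample size.** With 14/15 and 5/15: 7.849 × 1.2667 / (0.60)² = 27.62, against 27.47. The pooled-null, square-root and conditional binomial formulas still round up to 26. Nothing moves.

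**5. If the pilot were reused.** Assume 15 pilot patients per group with 14 and 5 interruptions, all counted in the 54, and no treatment effect. Two different questions can be asked.

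| Question | Chance of a significant result |
|---|---|
| Given that the pilot showed 14 vs 5, with 12 more per group, common rate 0.33 to 0.93 (negative binomial test) | 32% to 21% |
| Over all possible pilots, size set from the pilot effect by the formula in step 1, capped at 37 or 54 per group (Poisson, Wald and likelihood ratio) | 4.9% to 6.9% |
| Same, capped at 100 or 200 per group | 6.3% to 7.8% |
| No reuse, 27 new patients per group (Poisson, Wald and likelihood ratio) | 3.9% to 5.6% |

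The last three rows come from 1,000,000 runs per rate, with the group size never below the 15 already treated. The first row cannot be compared with a 5% level. The pilot split of 14 vs 5 has an exact p-value of 0.064 (rate ratio 0.36, 95% CI 0.10 to 1.05), and any valid trial has a raised chance of rejection once its first part is known to lie that close to significance. The like-for-like comparison is between the second and third rows and the fourth: a rise of at most about 3 percentage points.

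**The case for a change.** The strongest case for acting is that the text leaves matters open on every reading. On the per-surgery reading the number 15 is inconsistent with the two rates. On the per-time reading, which the duration offset makes possible, 27 per group has 80% power only if a case lasts about one unit on average, and no unit is given. The pilot has both trial arms, is absent from the protocol, and underlies a primary outcome and sample size different from the protocol's. Two sentences would settle it.

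The arithmetic stands, and so does the silence on split, unit and overlap. The rest is weaker. The SAP calls the calculation a priori and the data a pilot, which ordinarily means separate data that came first. The protocol predates the SAP by two and a half years and planned a different primary outcome, so its silence says little about a pilot run in between. Harm from reuse needs both a pilot of 30 and all 30 counted in the 54, and no sentence supports either. Reproducing 27 shows only that exposure was set to one; it does not show that the rates were raw per-surgery means.

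One limit remains: the like-for-like figures do not cover a choice of primary outcome made after seeing the pilot. That is a separate question, which the number 15 cannot answer.

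**Conclusion.** The inconsistency is real on the plain reading but does not reach the design. The best explanation is a clerical slip, 15 per group written as 15, or a rate that is not a raw per-surgery mean. Under the first, the required size goes from 27.5 to 27.6 per group and the plan's 27 is unaffected. The trial would recruit, analyse and test in the same way whichever explanation is true.

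The missing unit, split and pilot status are reporting gaps that can be filled from the pilot records when results are written up. Overlap between pilot and trial patients is not shown. If it had occurred in full, the level of the primary test would be about 5% to 8% rather than 4% to 6%, assuming Poisson counts, a common rate of 0.33 to 0.93 and a size set by the rate-difference formula. No change to the plan follows.

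### Does sizing on a Poisson model undermine the stated 80% power when interruptions are analysed by negative binomial regression?

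*SAP*

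**What the plan says.** The second paragraph of the SAP names the primary outcome ("The primary aim was surgical interruptions") and gives the planning rates: "A priori power calculation based on 15 pilot surgeries demonstrated the frequency of interruptions in the control to be 0.93 and 0.33 in THRIVE". The target follows from them: "Assuming a Poisson regression, 80% power, and 95% confidence interval, 27 patients in each group (54 total) were needed to demonstrate a significant difference". A reserve is added: "To account for incomplete data and dropouts, an additional 20 patients (74 total) were targeted for consent".

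The final paragraph describes the analysis: "Outcomes were calculated using negative binomial regression with case duration as an offset in the unadjusted and adjusted models". Only transcutaneous carbon dioxide is excepted, so interruptions are covered. It adds: "Models were adjusted for postoperative diagnoses". The SAP states neither a negative binomial dispersion nor a power figure under that model.

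The sample size in section 8 of the protocol concerns a different outcome, desaturation, and has no bearing on this point.

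**The concern.** A Poisson model sets the variance of the count equal to its mean. A negative binomial model lets the variance exceed the mean, as happens when some children need repeated airway support and others need none. If such clustering exists, each patient carries less information than the Poisson calculation assumed, and 27 per group yields less than 80% power. At fixed rates and a fixed number of patients the error can run only one way, because the negative binomial model does not allow a variance below the mean.

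The 80% is the SAP's only power figure for the primary outcome. If it were clearly too high, a reader faced with a non-significant result would credit the trial with more ability to detect the effect than it had.

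**Working it through.** **Inputs from the SAP.** Rates 0.93 (control) and 0.33 (THRIVE) interruptions per case; 80% power; two-sided 5%, inferred from the 95% confidence interval; 27 per group; 74 consented, which is 37 per group if split equally with none lost.

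**Input not in the SAP.** Dispersion k, where variance = mean + k × mean². It is assumed here at 0, 0.25, 0.5 and 1.0. At the control rate of 0.93 these give variances of 0.93, 1.15, 1.36 and 1.79.

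**Step 1: the SAP's own figure.** For a difference of two Poisson rates,

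n per group = (1.960 + 0.842)² × (0.93 + 0.33) / (0.93 − 0.33)² = 7.85 × 1.26 / 0.36 = 27.5.

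Other standard forms give 25.2 (log rate ratio, null-pooled variance), 25.8 (square-root scale) and 30.0 (log rate ratio, Wald). One-sided versions give 20 to 24, so two-sided 5% is the right reading. The 27 is sound for the model that the SAP names.

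**Step 2: power under the analysis model.** Gamma-Poisson counts were simulated at the pilot rates with equal durations and no covariates. The negative binomial model was fitted by maximum likelihood with k estimated, using 20,000 trials per cell. Likelihood-ratio power:

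| Evaluable per group | k = 0 | k = 0.25 | k = 0.5 | k = 1.0 |
|---|---|---|---|---|
| 27 | 80.5% | 75.3% | 70.0% | 61.7% |
| 31 (12 of 74 lost) | 85.2% | 80.8% | 76.2% | 67.4% |
| 37 (none lost) | 90.2% | 87.0% | 83.2% | 75.1% |

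Wald tests differ by about one point at most (79.4% at 27 per group and k = 0). Separate, smaller simulations gave 60% to 62% in the cell for 27 per group and k = 1.0, so about 61% is a fair summary.

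At k = 0 and 27 per group a Poisson fit gives 82.6% (likelihood-ratio) or 81.1% (Wald). Estimating a dispersion therefore costs about 2 points. Part of that reflects test size: with both rates at 0.63 and k = 0, simulated type I error was 4.8%/4.3% for negative binomial against 5.4%/4.8% for Poisson. Either way, the negative binomial model at k = 0 returns about the stated 80%.

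**Step 3: the model as planned.** The SAP's model has a duration offset and a diagnosis adjustment. Assume durations with a coefficient of variation of 0.5 and three equally common diagnosis levels with rate multipliers 0.5, 1 and 1.5. Power for k = 0, 0.25, 0.5 and 1.0 is then 77.8%, 70.6%, 67.5% and 55.6% at 27 per group, and 90.1%, 84.6%, 79.6% and 69.4% at 37 (4,000 trials). None of these inputs is in the documents. For a given residual k, power is 0 to 6 points below the table in step 2. The offset and adjustment may, however, also make residual k smaller than raw k, by an amount that the documents do not let one compute.

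**Step 4: the pilot rates.** At 27 per group and k = 0, a THRIVE rate of 0.43 in place of 0.33 gives about 58% power, and 0.23 gives about 93%. If the pilot had 15 cases per group (14/15 = 0.93 and 5/15 = 0.33, an assumption the text does not confirm), the Poisson standard error of the 0.60 difference is √(0.93/15 + 0.33/15) = 0.29. Shifts of 0.10 in one rate are then well within the pilot's imprecision.

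**Step 5: what the negative binomial model protects.** With 27 per group and no true effect, the Poisson Wald test rejected in about 8% of simulated trials at k = 0.5 and 12% at k = 1.0, against about 6% for negative binomial.

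**The case for a change.** The best case for a change is this. The SAP's one power figure belongs to a model it does not use for the primary outcome. At the pilot rates with 27 evaluable per group, the figure is in effect a ceiling. The reserve of 20 is assigned to losses, not to dispersion. One added sentence would correct the record at no cost to the trial.

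The mismatch stands, and so does its direction at fixed rates and fixed numbers. It is also true that the reserve does not cover every case: at k = 1.0 power is about 75% even with none of the 74 lost.

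The rest does not carry. The SAP discloses its condition in the same sentence as the figure ("Assuming a Poisson regression, 80% power, and 95% confidence interval"), so nothing false is asserted. Any shortfall depends on a dispersion that the documents do not give, and they do not show that over-dispersion exists. The added sentence would have to choose between two unsatisfactory sets of figures. Those for equal durations and no covariates again describe a model other than the planned one. Those for the offset-and-adjusted model rest on invented durations and diagnosis effects. A table of power by assumed dispersion would also look more precise than the pilot rates allow, since a shift of 0.10 in one rate moves power from 58% to 93%.

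**Conclusion.** No change to the plan follows. Sizing on Poisson and analysing by negative binomial regression is a disclosed simplification and a fair trade-off: the planning calculation is simple and correct on its own terms, and the analysis guards against a false-positive rate that a Poisson fit would let rise if counts cluster.

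At the exact pilot rates with only 27 evaluable per group, power is about 80% with no residual dispersion and about 75%, 70% and 61% at assumed values of 0.25, 0.5 and 1.0 (equal durations, no covariates). With all 74 evaluable it stays above 80% up to a dispersion of 0.5. Under the assumed offset and adjustment it is just below 80% at that value. The documents do not establish where the trial sits in this range, so no shortfall is demonstrated.

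The mismatch does not bias the rate ratio or invalidate the test. The SAP is written in the past tense and reports a decision taken after an interim analysis, so a recalculated planning power would have little practical use. A reader weighing a non-significant result should use the confidence interval for the rate ratio, which reflects the dispersion estimated from the trial's own data.

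### Does the SAP's 20-patient allowance, with no stated analysis set or missing-data rule, put the primary comparison at risk?

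*SAP*

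**What the plan says.** The SAP's second paragraph takes pilot rates, "the frequency of interruptions in the control to be 0.93 and 0.33 in THRIVE", and concludes that "27 patients in each group (54 total) were needed to demonstrate a significant difference". It then adds a margin: "To account for incomplete data and dropouts, an additional 20 patients (74 total) were targeted for consent".

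The third paragraph defines the primary outcome: "Interruptions were defined as the need to pause surgery to provide airway support, such as mask ventilation or intermittent intubation". The fourth gives the model: "Outcomes were calculated using negative binomial regression with case duration as an offset in the unadjusted and adjusted models", with tCO2 excepted, and adds: "Models were adjusted for postoperative diagnoses".

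On allocation, protocol section 8 states: "At the time of enrollment, patients will be randomized to control or intervention arms using a random number generator". The SAP does not say when allocation took place.

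Neither document names an analysis set, defines a dropout, states how an incomplete record is treated, or plans a sensitivity analysis for missing data.

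On eligibility, the SAP's first paragraph reads: "Exclusion criteria included papillomatosis, tracheostomy, or unrepaired heart disease". The protocol's list in section 8 names neither papillomatosis nor tracheostomy and words its cardiac criterion differently. No date or reason is given for the difference.

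**The concern.** A regression with one record per patient and no imputation leaves out, by default, anyone who lacks the outcome or the offset, and in the adjusted model anyone who lacks a diagnosis. If allocation happens at enrolment, as the protocol says, those left out are randomised patients. Randomisation protects the comparison only if the omitted patients do not differ between arms in ways linked to interruptions.

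The setting makes such a link conceivable. Treatment and outcome occur in the same short procedure, so a case in which the assigned technique is abandoned might be recorded either as an event or as a loss. A margin of 27% would be large enough to matter. The differing exclusion lists raise a related worry, that patients were removed after allocation under criteria added later.

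**Working it through.** **Inputs.** Rates of 0.93 (control) and 0.33 (THRIVE) per case, 27 per arm, and 74 consented are from the SAP's second paragraph. Assumptions not in the documents: all 74 randomised, 37 per arm; equal case durations; Poisson counts; two-sided 5% test.

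**The plan's own figures.** The rate-difference formula gives n = (1.96 + 0.84)² × (0.93 + 0.33)/(0.93 − 0.33)² = 27.5 per arm, next to the stated 27. Simulated Poisson power at 27 per arm is about 82% with a likelihood-ratio test. The allowance is 20/74 = 27.0%, and 54/(1 − 0.27) = 74.

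**Planned effect, 27 + 27 analysed.** Expected events are 27 × 0.93 = 25.11 and 27 × 0.33 = 8.91. The rate ratio is 0.33/0.93 = 0.355, and z = ln(0.93/0.33)/√(1/25.11 + 1/8.91) = 2.66, p = 0.008.

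**All 74 counted, lost controls at 0.93.** Let k patients be lost per arm and let the lost THRIVE patients average x. Then C = 37 × 0.93 = 34.41, T = (37 − k) × 0.33 + kx, and z = ln(C/T)/√(1/C + 1/T).

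For k = 10:

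| x | T | Rate ratio | z | p |
|---|---|---|---|---|
| 0.33 | 12.21 | 0.355 | 3.11 | 0.002 |
| 0.93 | 18.21 | 0.529 | 2.20 | 0.028 |
| 1.09 | 19.81 | 0.576 | 1.96 | 0.05 |

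So even if THRIVE did nothing for the ten lost patients (x = 0.93), the result would stay significant.

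Significance is lost when T reaches about 19.8. Solving for x at smaller k:

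| Lost per arm | x at which significance is lost | Multiple of 0.33 |
|---|---|---|
| 10 | 1.09 | 3.3 |
| 5 | 1.85 | 5.6 |
| 3 | 2.86 | 8.7 |
| 2 | 4.12 | 12.5 |

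**No true effect, control loss unrelated to outcome.** If the ten lost THRIVE patients averaged m, the analysed THRIVE mean is (34.41 − 10m)/27.

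| m | Analysed mean | Rate ratio | False-significance rate (simulated) |
|---|---|---|---|
| 0 | 1.274 | 1.37 | 23% |
| 0.93 | 0.93 | 1.00 | 5% |
| 1.86 | 0.586 | 0.63 | 31% |

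With five lost, the extremes are 1.16 and 0.84, with rates of 9% and 10%. The same kind of loss in both arms cancels.

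**What the 20 can be.** The margin is attached to consent, so it can include patients who never reached allocation or the procedure. The SAP also collects oximetry by the second, tCO2 at two times and adverse events before discharge. A patient lacking any of these has incomplete data but can still supply an interruption count and a duration, and so stays in the primary model. A procedure cut short also stays in, because the offset credits the time observed.

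**Abandoned technique.** The outcome definition covers a pause for mask ventilation or intubation. Rescue that stops surgery is therefore an event on the face of the text, and no sentence reclassifies it as a loss.

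**The case for a change.** The best case for acting is that a plan providing for this much loss ought to say what happens to those lost, and that doing so needs only a few sentences and no extra patients. The protocol's timing of allocation allows losses after randomisation. At the full allowance the threshold of 1.09 is only 0.16 above the planned control rate. It also falls if the lost controls did well: with lost controls at 0.33 and lost THRIVE patients at 0.93, the rate ratio is 0.64 (95% CI 0.36 to 1.15). Overdispersion, which the negative binomial model allows for, would widen the intervals further.

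The silence and the arithmetic both stand. What does not stand is the step to a defect. The SAP nowhere restricts its regressions to complete records; that is software default, not a stated rule. The damaging scenarios need all 20 to be randomised and missing the primary outcome, and the loss to be related to interruptions differently in the two arms. The documents give no sign of either.

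The eligibility difference is also real, but it is a separate question of reconciling two documents. The SAP's verb may mark a partial list, the ordinary reading is that these were enrolment criteria, and nothing shows that an allocated patient was removed. Reconciling the lists would not alter this analysis.

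**Conclusion.** No change to the plan follows. This is a gap in written detail that analysts ordinarily fill sensibly: analyse patients in the arm to which they were allocated, count interruptions after any change of technique, and show losses by arm and reason in a flow table. No stated rule is shown to produce a wrong answer, and a compulsory tipping-point analysis would be an addition of preference until actual loss of the primary outcome is known to be material.

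With lost controls at the planned 0.93, the conclusion at the planned effect is reversed only if lost THRIVE patients averaged at least 1.09 interruptions with 10 lost per arm, or 1.85 with 5. Those figures rest on 37 randomised per arm, Poisson counts and equal durations; they would be lower if lost controls had fewer interruptions or counts were overdispersed. I would reconsider if the trial's flow showed primary-outcome loss near the full allowance and unbalanced between arms, or patients taken out after allocation.

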Scientific Protocol

**Transnasal Humidified Rapid-Insufflation Ventilatory Exchange (THRIVE) Use in
Pediatric Populations**

Scientific Protocol

NCT03430206

January 9, 2018

1) Name of study

Transnasal Humidified Rapid-Insufflation Ventilatory Exchange (THRIVE) Use in Pediatric Populations

2) PI and other key investigators or key study personnel

[name] – PD

[name] – COPD

[name] – other personnel

[name] - other personnel

[name] - other personnel

[name] – other personnel

[name] – other personnel

[name] - other personnel

3) Specific source of institutional funding (account number)

none

4) List of sources from whom you are seeking funds (or have sought funding) for this project

none

5) Specific aims and basic hypothesis including an explicit primary hypothesis or goal

Hypothesis: The application of THRIVE at 1-2L/kg/min up to 70L/min will reduce to incidence of desaturation events (defined by SpO₂ <90%) by 75%.

Secondary aims: to verify the safety of intraoperative use of THRIVE in pediatric populations in the operating room and assess the incidence of adverse effects.

6) General background (2 page maximum including published preclinical and animal data supporting basic hypothesis, if relevant)

The introduction of high-flow nasal cannula (HFNC) as Transnasal Humidified Rapid-Insufflation Ventilatory Exchange (THRIVE) to the operating theater has been demonstrated and validated in numerous studies in both adult and pediatric patients prior to intubation.^{1,2,3} It has including those undergoing laryngeal procedures and surgeries, to augment sedation-related hypoventilation, or as a substitute for apneic oxygenation, intermittent intubation or mask ventilation, or jet ventilation.^{4,5,6} Given the previously demonstrated safety and efficacy of high-flow nasal cannula in similar populations, we intend to study its use during relevant procedures.

7) Preliminary unpublished data (1 page maximum)

At Lucile Packard Children’s Hospital in 2017, a retrospective analysis of 3 months of eligible cases (pediatric patients undergoing microdirect laryngoscopy and bronchoscopy (MDLB) with or without other airway interventions in pediatric patients undergoing general anesthesia with a

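### As written, the SAP's case-duration offset compares adverse events recorded up to discharge as rates per unit of operating time, and neither document states a per-patient comparison

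*SAP*

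**What the plan says.** The last paragraph of the SAP sets one model for the outcomes: "Outcomes were calculated using negative binomial regression with case duration as an offset in the unadjusted and adjusted models, with the exception of" transcutaneous CO2. It adds: "Models were adjusted for postoperative diagnoses". No other outcome is exempted.

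Adverse events are among the outcomes to be compared. The SAP's list of secondary aims ("The secondary aims were to compare differences in oxygen desaturation index (ODI), desaturations below 90%, transcutaneous carbon dioxide") ends with them. The outcome definitions paragraph says how they were collected: "Adverse events (nausea, vomiting, sinus pain, throat pain, epistaxis) were recorded prior to discharge".

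The primary outcome is of a different kind: "Interruptions were defined as the need to pause surgery to provide airway support, such as mask ventilation or intermittent intubation". The pilot is said to have shown "the frequency of interruptions in the control to be 0.93 and 0.33 in THRIVE".

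In the protocol, the secondary aims in section 5 are to verify safety and to "assess the incidence of adverse effects". The protocol does not list the five symptoms, does not say that incidence is per patient, and gives no analysis for adverse events.

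**The concern.** An offset fixes the coefficient of log duration at 1, so the model takes the expected number of events to be proportional to case length. That suits interruptions and ODI events, which can occur only while the case is running. Nausea, vomiting, sinus pain, throat pain and epistaxis were recorded before discharge. Whether that means continuous recording or a single check, the length of the operation is not the window in which they were ascertained, and the SAP offers no argument for proportionality. One event after a 15-minute case counts as four times the rate of one event after a 60-minute case (60/15 = 4).

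Two things are at stake. The modelled quantity, events per minute of surgery, is not the proportion of patients affected, which is what a clinician would want from a safety aim worded as incidence. Case duration is also measured after randomisation and may itself depend on the arm. An interruption is by definition a pause in surgery, and the trial is sized to show fewer of them with THRIVE. If recorded duration includes the pauses, a real effect on the primary outcome would shorten THRIVE cases and raise the THRIVE adverse event ratio with no change in any patient's risk.

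**Working it through.** **The plan's own figure.** The SAP gives no figure for adverse events. Its only sample size is 27 per group for interruptions (Poisson regression, 80% power, two-sided 5% assumed). The rate-difference formula, with one unit of exposure per patient, gives

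n = (1.960 + 0.842)² × (0.93 + 0.33)/(0.93 − 0.33)² = 7.849 × 1.26/0.36 = 27.5, so 28.

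The square-root transform gives 25.8 and the log rate ratio with pooled null variance gives 25.2, so 26 for each. The stated 27 is thus reproduced to within rounding and choice of formula. This is consistent with reading 0.93 and 0.33 as mean interruptions per case, although the SAP gives no units. I use 27 per arm below.

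**What the offset does.** With no overdispersion, the fitted ratio is

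(events/total minutes, THRIVE) ÷ (events/total minutes, control).

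With equal arm sizes and equal per-patient risk, it reduces to mean control duration ÷ mean THRIVE duration. Equal durations give 1.00.

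**Shorter THRIVE cases (illustration).** Assumptions, none of them in the documents: 0.93 and 0.33 are interruptions per case; recorded duration includes pauses; non-pause time is the same in both arms, at 20, 30 or 60 min; each pause lasts 2, 5 or 10 min. Duration = non-pause time + interruptions × pause length.

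| Non-pause time | 2 min per pause | 5 min per pause | 10 min per pause |
|---|---|---|---|
| 20 min | 21.86/20.66 = 1.06 | 24.65/21.65 = 1.14 | 29.30/23.30 = 1.26 |
| 30 min | 31.86/30.66 = 1.04 | 34.65/31.65 = 1.09 | 39.30/33.30 = 1.18 |
| 60 min | 61.86/60.66 = 1.02 | 64.65/61.65 = 1.05 | 69.30/63.30 = 1.10 |

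THRIVE cases are about 2% to 20% shorter across the grid. A true risk ratio of 0.75 would appear as 0.75 × 1.020 = 0.77 up to 0.75 × 1.258 = 0.94.

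**Longer THRIVE cases.** The same identity works in reverse. If THRIVE cases were 10% or 20% longer, the ratio at equal risk would be 1/1.1 = 0.91 or 1/1.2 = 0.83. With cases 20% longer, a true risk ratio of 1.25 would appear as 1.25/1.2 = 1.04.

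**Against sampling error.** Take 5/27 in each arm at the largest shift in the grid. The ratio is 29.30/23.30 = 1.258, the standard error of its log is √(1/5 + 1/5) = 0.632, and the 95% CI is 1.258 × exp(±1.96 × 0.632) = 0.36 to 4.34.

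**False finding of harm.** Exact binomial enumeration with 27 per arm, equal risk, events scored yes/no, a two-sided 5% Poisson Wald test, and tables with an empty arm counted as non-significant:

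| Shift in ratio | 20% risk | 30% risk |
|---|---|---|
| 1.00 | 0.6% | 0.7% |
| 1.14 | 1.1% | 1.4% |
| 1.26 | 2.4% | 2.9% |

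The nominal rate in one direction is 2.5%. At 40% risk and the largest shift the figure is 3.1%.

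**The case against.** The strongest reply is that a rate is not wrong in itself. Study oxygen is delivered during the procedure, so case duration roughly tracks exposure to it, and exposure-adjusted rates are a recognised safety measure. That stands as far as it goes: operating time could be defended as the exposure. But the SAP does not defend it, and the symptoms were not ascertained over that time.

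A reader might infer that the SAP contradicts the protocol. The documents do not support so much. Section 5 of the protocol says incidence without saying per patient, and section 9 counts desaturation, an intraoperative event, among adverse events. A per-patient reading is still the natural one, since section 7 reports desaturation as a share of patients (24/44), but it is a reading. Nor does either document rank adverse events as the main safety comparison; the SAP lists them as one of four secondary aims.

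A reader might also infer that the offset biases the trial against THRIVE. That needs every assumption of the grid, including equal non-pause time in the two arms, and no duration is reported. If THRIVE cases ran longer, the error would change direction and could conceal harm.

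Finally, the SAP is short and in the past tense. Adverse events may have been tabulated separately without mention. That is why the point is confined to the plan as written.

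**Conclusion.** The point holds as a mismatch between the model and the outcome. Read literally, the SAP compares adverse events per unit of operating time, without justification, and no per-patient comparison is stated. This part depends on no assumed minutes and remains true when durations are equal.

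The distortion between arms is conditional and probably modest. It is nil on average with equal durations, 1.02 to 1.26 under the assumptions listed, and in the other direction if THRIVE cases are longer. It is smaller than sampling error with 27 per arm. The harm is to the estimate more than to the test: the false-harm probability at the largest shift is close to nominal, slightly below 2.5% at 20% risk and slightly above at 30%. It would be too strong to say that the error rate is materially inflated, or that it always stays below nominal. The matter concerns a secondary safety outcome; the primary outcome and the 27 per group are unaffected. It should be corrected, and my confidence is medium because the documents give no durations or event rates.

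**What to change.** Exempt adverse events from the duration offset and keep that model for intraoperative counts: interruptions and ODI events. State that each adverse event is scored yes or no per patient. For each event, and for any event, report the number and percentage of patients by arm with a between-arm difference and 95% CI; an exact risk difference is one suitable choice. If the sponsor prefers to keep a rate per operating time, the SAP should justify it, and the per-patient table should stand beside it.

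No new data are needed. The SAP already reports an interim analysis, so a change made after the data were seen must be labelled post hoc. The cost is that the simple comparison loses the adjustment for postoperative diagnosis, and exact intervals are somewhat conservative.
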